15.2 Data analysis plan

The primary goal of the analysis is to study the effect of the treatment on the outcome variables, in consideration of other covariates, including the demographic information and medical history of the participants and dialysis centers, which can potentially interact with the treatment. First, we will do an exploratory analysis of all the covariates altogether and stratified in the treatment and control group. We will study the effect of each of these covariates separately and together on the outcome. In the comprehensive study of all factors, we will build several models, including both parametric and tree-based models. We will also consider relevant interaction between the independent variables in the model. For the parametric models, we will use logistic regression for the binary outcomes, general linear regression (after a possible transformation of some covariates) for the continuous outcomes, Poisson regression with an over-dispersion test or a general log-linear model, for count outcomes, and a multinomial regression for the categorical variables with more than two categories. We will assess the fitted models based on model diagnostics and goodness-of-fit/prediction measures, such as adjusted R^2 , AIC, BIC, and cross-validation. A follow-up analysis will be done based on the results obtained from the various regression models. All the significant first-order and interaction effects will be further analyzed to understand the nature of the effect, and possibly considering further models stratified by relevant covariates.

Interim analyses will be done at least in the interval of 1, 3, and 6 months for the purpose of monitoring, presentations to the monitoring board, and any remedies (as needed) to ensure the quality of the study and safeguard the study population.

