8.2 Secondary Efficacy Endpoints

The secondary efficacy endpoints are:

1. Need for hospitalization
 - This is defined by documentation in the case report form (CRF) of physician referral to hospital for admission
2. Hospital length of stay
 - The number of overnight stays in the hospital, entered into the CRF
3. ICU admission
 - Documentation in the CRF of physician recommendation for ICU transfer.
4. ICU length of stay
 - The number of overnight stays in the ICU
5. Mechanical ventilation
 - Documentation in the CRF of administration of mechanical respiratory assistance and length of time such assistance required
6. Duration of mechanical ventilation
 - Documented in the CRF by physician
7. Recovery time from COVID-19
 - Defined as testing negative, plus the time for full recovery as determined by physician
 - Documented in the CRF by physician
8. Change in any existing comorbidities (e.g., worsening congestive heart failure) or newly diagnosed disease
 - Documented in the CRF by physician
9. Incidence of secondary non-COVID-19 infections (relapses, superinfections and new infections).
 - Documented in the CRF by physician
10. Change in T lymphocyte subsets (CD4, CD8)
 - Samples taken at enrollment, at 8 weeks and at 6 months, or at time of hospital admission if that is required
11. Mortality
 - COVID-19 related, or non-COVID-19 related; documented in the CRF by physician.

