Each sample size calculation depends on the type of endpoints, the variability of data, analysis methods used, and the minimal difference (or effect size) that we wish to be able to detect between the treatment (with Zadaxin) or control (without Zadaxin) groups. There are four types of endpoints for this study, dichotomous (e.g., infection of COVID19, the primary endpoint; ICU admission; or mortality), polytomous (e.g., health changes: no change, moderate, severe changes), counts (e.g., occurrence of non-COVID-19 infections), or continuous outcome variables (e.g., CD4, CD8, CD4/CD8, length of hospital stay, recovery time from COVID19). For a dichotomous outcome, a suitable model is a logistic regression with the treatment status (treated or not treated with Zadaxin) as the primary covariate, demographic information (age, gender, race), health/medical information (e.g., Karnofsky score, co-morbidity, and other biomarkers) and environmental information (treatment center, among others) as other relevant covariates. Assume the infection rate for the control group is about 0.40 and with a significance level of 0.05 (unless specified otherwise), if we use a simple logistic regression, a sample of size 200 will be able to detect a change at least at 0.185 in the infection rates between the treatment and control groups with a power of 80%. If we have a bigger sample size, say 234, we would be able to detect a change with a minimal difference of 0.17 with the same power or a minimum difference of 0.185 with a power of 86.5%. Using more comprehensive procedures (below) or if the actual difference is (much) larger than the minimal difference, we will have a (much) higher power than 80% to detect the actual difference. If we make a conservative adjustment for multiple comparisons incorporating other covariates after a pre-screening step, at an adjusted significance level 0.005, a sample of size 205 will provide 80% power for detecting a change of at least as large as 0.23. Using a multiple logistic regression model that takes into account the correlation among the various covariates, say if the correlation is 0.2, we can detect a minimal difference at 0.202 with a sample size of 200. If the correlation is 0.5, the minimum detectable difference would be 0.25. The highly correlated covariates that lead to multicollinearity will indicate the need for removal of redundant covariates in modeling the endpoint, and the removal will lead to more degrees of freedom in our study and the same power in detecting the even smaller difference. We will use all the sample we have and incorporate censored data or treat missing information with survival or a more comprehensive model than the logistic regression; thus, we expect to be able to detect a smaller minimal difference or have a much higher power to detect the actual difference in the infection rates than given above.

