
For a continuous endpoint, with a sample size of 201, using the simplest testing procedure (with a possible transformation of the endpoint variable), we will be able to detect an effect size at least at 0.35 between the treatment and control groups with a power of 80%. Since we will use a general linear model to delineate the effects or variations due to covariates/factors, we expect to be able to detect a smaller minimal effect size or a higher power to detect the actual difference that is bigger than the minimal effect size. In a very conservative sense, comparing a polytomous response between treatment and control can be viewed as a multiple testing problem of comparing proportions for each of the categories. For response variables with three categories, if the proportion of a certain category is approximately 0.3, a sample of size 202 will enable us to detect a minimal change of 0.19 with a power of 80%. We emphasize that this calculation is very conservative, and we expect have much better performance, both in terms of detection of smaller departure and having better power. For the ordinal polytomus outcome, we are interested in

identifying if the treatment improves the proportion of different categories of the outcome than that of control. Assume that the response has 3 categories with equal proportion in the overall population (averaged over control and treatment). With a sample size of 200 we can detect a minimal improvement of size 0.725 in the overall odds ratio with 80% power. The count variables can be modeled as continuous with appropriate transformation and the sample size justification will be similar to that of a continuous response.

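### Name the enrolment CD4 and CD8 value as a fixed covariate for the T-cell endpoint: if it is left out, power falls by about 9 to 12 points at an assumed correlation of 0.5

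*Combined protocol and SAP*

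**What the plan says.** Section 8.2, item 10, defines the endpoint as "Change in T lymphocyte subsets (CD4, CD8") and gives the sampling times: "Samples taken at enrollment, at 8 weeks and at 6 months, or at time of hospital admission if that is required". Sections 11.1 and 12.2 and Table 1 confirm that every subject has a draw before treatment.

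Section 15.1 treats these measures as "continuous outcome variables (e.g., CD4, CD8, CD4/CD8, length of hospital stay, recovery time from COVID19"). The CD4/CD8 ratio appears there and in section 11.1, although item 10 itself names only CD4 and CD8. For continuous endpoints with 201 subjects and 80% power, section 15.1 puts the detectable effect size at 0.35, on this basis: "using the simplest testing procedure (with a possible transformation of the endpoint variable), we will be able to detect an effect size at least at". It then expects a general linear model with covariates to do better, but names no covariate.

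Section 15.2 assigns "general linear regression (after a possible transformation of some covariates) for the continuous outcomes". It describes the covariates this way: "in consideration of other covariates, including the demographic information and medical history of the participants and dialysis centers, which can potentially interact with the treatment". Unspecified biomarkers are mentioned only in section 15.1, in the logistic model for dichotomous outcomes. No section says whether the modelled T-cell outcome is the change or the follow-up value.

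**The concern.** When an outcome is measured before and after randomisation, its own baseline value is often the strongest predictor of follow-up. A linear model that includes it (ANCOVA) is at least as precise as an unadjusted change score or an unadjusted follow-up value, apart from one degree of freedom. Here the baseline is collected from everyone but not named in the model.

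Two things are at stake. An unadjusted analysis has a larger standard error, so a real T-cell effect of the planned size is more likely to be missed. And a change score is negatively correlated with baseline when the two variances are equal, so a chance difference between arms at enrolment moves the estimate in this one trial.

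Section 15.2 also foresees several parametric and tree-based models, compared by fit and prediction criteria, and section 15.1 foresees removing correlated covariates. In a trial without placebo, the baseline term could therefore enter or leave the model after outcomes are known.

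**Working it through.** **Inputs from the documents:** 1:1 allocation (10.5); about 200 subjects with complete data (15.1); effect size 0.35, 80% power and total N = 201 for a continuous endpoint (15.1); significance level 0.05, sidedness not stated (15.1).

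**Assumptions:** the correlation rho between enrolment and follow-up is not given for CD4 or CD8, so 0.5 is used with a range of 0.3 to 0.8. (The 0.5 in section 15.1 is a correlation among covariates in the logistic model, a different quantity.) Equal variances at both times are assumed.

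**Step 1, the plan's own figure.** Two-sample t-test, noncentrality d × sqrt(N/4). At N = 201 and d = 0.35 this is 0.35 × sqrt(50.25) = 2.48.
- One-sided 0.05: power 79.6%. This reproduces the stated 80%.
- Two-sided 0.05: power 69.5%. This does not.

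Both bases are therefore carried forward.

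**Step 2, variances, with the follow-up SD set to 1.**
- Raw follow-up value: 1
- Change score: 2(1 − rho)
- ANCOVA: 1 − rho²
- ANCOVA relative to change score: (1 − rho²) / [2(1 − rho)] = (1 + rho)/2

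At rho = 0.5, the change score and the raw value both have variance 1 and ANCOVA has 0.75. The effective effect size becomes 0.35 / sqrt(0.75) = 0.404.

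**Step 3, power at N = 200 and rho = 0.5.**

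| Test at 0.05 | Baseline left out | Baseline included | Difference |
|---|---|---|---|
| Two-sided | 69.2% | 81.2% | about 12 points |
| One-sided | 79.4% | 88.6% | about 9 points |

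**Step 4, sensitivity to rho, comparator and units (two-sided, N = 200).** The plan does not say in which SD its 0.35 is expressed, so the change-score comparison is shown both ways.

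| Comparison | rho 0.3 | rho 0.5 | rho 0.8 |
|---|---|---|---|
| Change score, 0.35 in change-score SDs | 69.2 → 86.3% (17 points) | 69.2 → 81.2% (12) | 69.2 → 73.8% (5) |
| Change score, 0.35 in follow-up SDs | 54.8 → 73.3% (18) | 69.2 → 81.2% (12) | 97.3 → 98.4% (1) |
| Raw follow-up value, 0.35 in follow-up SDs | 69.2 → 73.3% (4) | 69.2 → 81.2% (12) | 69.2 → 98.4% (29) |

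The two unadjusted analyses lose most at opposite ends of the range. Since the plan does not say which it would use, no value of rho in this range makes both nearly free of loss.

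**Step 5, chance imbalance.** With about 100 per arm, the SD of the baseline difference between arms is sqrt(4/200) = 0.14 SD, and its 95% range is ±1.96 × 0.14 = ±0.28 SD. At rho = 0.5, an imbalance of 0.28 SD shifts an unadjusted change score by (1 − 0.5) × 0.28 = 0.14 SD in the opposite direction. That is 0.14/0.35 = 40% of the target effect.

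**The case against.** The strongest reply is that the plan's silence is not an exclusion. The covariate list is open, section 15.1 commits continuous endpoints to a covariate-adjusted linear model, and a baseline that predicts follow-up well would probably be selected if offered. This stands. A reader might infer that the plan commits to an unadjusted analysis and so gives up 12 points of power. The documents do not support that: they leave the matter open, and the loss is conditional. But selection by fit after the data are seen does not replace a term fixed in advance.

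Second, the size rests on assumptions. This also stands. Rho of 0.5 has no source in the documents, and 12 points is a two-sided figure that starts from 69%, not from the stated 80%. Item 10 is worded as a change, so the change score is the natural comparator, and against it the loss shrinks to 1 to 5 points at rho of 0.8.

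Third, a reader might infer that chance imbalance biases the result. It does not: under randomisation the unadjusted estimate is unbiased over repeated trials, and the issue is precision. Nor do the documents support calling CD4 and CD8 the only direct readout of the drug's mechanism. Section 5.2 describes that mechanism through other pathways, and section 11.1 also plans COVID-19 antibody testing on stored serum.

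Finally, this is one of eleven secondary endpoints in a self-described pilot, and section 15.2 fixes a final covariate set for no endpoint. That limits the weight of the point but does not remove it.

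**Conclusion.** The point holds as a nearly free improvement to secondary endpoint 10. The enrolment value is measured in everyone and is not named in the continuous-outcome model, and adjustment is neither specified nor excluded. If it is left out, the cost at N = 200, effect 0.35 and an assumed rho of 0.5 is about 12 points of power two-sided (69% against 81%) or about 9 points one-sided (79% against 89%). Across rho of 0.3 to 0.8 the two-sided loss runs from about 1 to 29 points, depending on comparator and SD units. One trial's estimate is also more exposed to chance imbalance, without bias over repeated randomisation. The primary COVID-19 infection result is unaffected.

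**What to change.** Add to section 15.2: 'CD4, CD8 and CD4/CD8 at week 8 will each be compared between randomised arms by a linear model with treatment, the enrolment value of the same measure and dialysis centre. These terms stay in the model regardless of significance or model selection. Outcome and baseline use the same transformation.' State whether the test is one- or two-sided. The treatment coefficient is the same whether the follow-up value or the change is entered, provided both are on that transformed scale.

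Apply the same model at month 6 once the schedule is reconciled. Sections 8.2, 11.1 and 12.7 include a month 6 subset draw, but Table 1, as it reads here, shows subsets only at screening, week 4 and week 8. State also how the alternative hospital-admission sample in item 10 is handled.

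The cost is one short addition to the text and one degree of freedom. The week 8 analysis needs no new samples, visits or subjects. A subject without an enrolment value needs a simple baseline imputation or drops out of this analysis, as would already happen with a change score.

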13.9 Data Safety Monitoring Board (DSMB)

Acknowledging the inherent vulnerability of our study population (older hemodialysis patients), a DSMB will be established with a mission to ensure that the interests of the patients entered in the trial are being well served (i.e., the risk-benefit ratio is appropriate) and that the scientific integrity of the trial is maintained from trial initiation to completion [21]. The DSMB will be comprised of three independent physicians with expertise in nephrology, geriatric medicine and infectious disease as well as one independent biostatistician. The committee will meet at trial initiation and quarterly for the one-year duration of the study.

The study will be stopped if the DSMB believes that the number or severity of treatment-related adverse events suggests that it is in the best interests of the patients to do so.

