15 STATISTICAL ANALYSIS

15.1 Sample size justification

It has been speculated that infection rates may be as high as 40% in the general population and for those over the age of 60 years, particularly those with underlying comorbidities, the rate may be higher. Further, patients who receive dialysis two or three times weekly at dialysis centers are more likely to be exposed to virus than the general elderly population. In as much as there are no existing data demonstrating the effects of Ta1 in prevention of COVID-19 infection, in this pilot project we have elected to sample 240 subjects, anticipating that 40 subjects will drop off study for any of a number of reasons. That will leave ~200 enrolled subjects with complete data availability. We justify the choice of sample size below.

Clinical Study Protocol: Ta1 to Prevent COVID-19 Infection in Elderly Renal Dialysis Patients

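### Section 15.2 does not single out one primary test of the infection endpoint, so the 5% error level behind the power figures in 15.1 is not controlled, and it gives no method for patients who drop out

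*Combined protocol and SAP*

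**What the plan says.** Section 6.1 sets a confirmatory aim: to demonstrate a lower incidence of COVID-19 infection over six months. Section 15.1 calls logistic regression, with treatment as the primary covariate, a suitable model for a dichotomous outcome. Its planning statement begins "Assume the infection rate for the control group is about 0.40", uses a significance level of 0.05, and gives 80% power for a difference of 0.185 with 200 subjects. A level of 0.005 appears there only as a conditional scenario after covariate pre-screening.

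Section 15.2 repeats logistic regression for binary outcomes and states no alpha. Its procedure is broader: "In the comprehensive study of all factors, we will build several models, including both parametric and tree-based models". Relevant interactions are considered, and models are assessed by adjusted R², AIC, BIC and cross-validation. Then "All the significant first-order and interaction effects will be further analyzed to understand the nature of the effect", possibly with further models stratified by covariates.

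On dropout, 15.1 expects to lose 40 of 240 subjects and says "That will leave ~200 enrolled subjects with complete data availability". It also says that the whole sample will be used and that the analysis will "incorporate censored data or treat missing information with survival or a more comprehensive model than the logistic regression". Section 15.2 lists no survival, censoring or missing-data method.

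On interim looks, 15.2 says "Interim analyses will be done at least in the interval of 1, 3, and 6 months", for monitoring, board presentations and remedies that protect study quality and participants. No boundary is given. The only stopping criterion in Section 13.9 concerns treatment-related adverse events.

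**The concern.** A power statement at 0.05 describes one test chosen in advance. Naming a model family does not make that choice. Within logistic regression the treatment effect can be tested unadjusted, with any subset of covariates, or inside an interaction model, and 15.1 adds survival or more comprehensive models as further options. If the reported result may be picked after seeing several fits, the chance of a nominally significant Ta1 finding under no effect exceeds 5% by an amount the plan leaves open. The trial is open-label, so the arms can be compared as data accrue, before a choice has been recorded.

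The dropout gap is a separate matter. Without a stated rule, a patient lost uninfected at month 2 might be excluded, counted as uninfected, imputed or censored. If loss differs by arm, those choices give different answers. Deaths raise the same question: the exclusion criteria cover anticipated survival under 3 months, while the objective runs to six.

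**Working it through.** **1. The plan's own figure.** Inputs from 15.1 and 10.5: control rate 0.40, treated rate 0.40 − 0.185 = 0.215, alpha 0.05, 80% power, 1:1 allocation. Sidedness is not stated; two-sided is tried here. With mean rate 0.3075:

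n per arm = [1.960·√(2·0.3075·0.6925) + 0.8416·√(0.40·0.60 + 0.215·0.785)]² / 0.185² = [1.2791 + 0.5381]² / 0.034225 = 96.5, so 97 per arm and N = 194 (stated: 200).

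Power at 100 per arm = Φ[(0.185·√100 − 1.2791)/0.6394] = Φ(0.893) = 81.4% (stated: 80%).

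The other infection-rate figures also reproduce as two-sided: a difference of 0.17 needs N = 234 (stated 234), and 0.23 at level 0.005 needs N = 204 (stated 205). The continuous-endpoint figure (N = 201, effect size 0.35, 80%) reproduces only as one-sided: 79.8%, against 69.9% two-sided. So sidedness is unstated and also not uniform across 15.1.

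**2. Choice among models, no true effect.** The documents give no number of covariates or models, so these are assumptions. Two logistic simulations with N = 200 and about 40% infected:

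| | 6 covariates plus site, 3,000 trials | 8 covariates, 1,500 trials |
|---|---|---|
| Single unadjusted test | 5.7% | 5.2% |
| Any treatment main-effect model | 8.0% (8 models) | 7.0% (3 models) |
| Any treatment interaction | 25.5% (6 tests) | 31.2% (8 tests) |
| Any of these | 31.1% | 36.4% |

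Simulation standard error for a 5% rate is √(0.05·0.95/3000) = 0.4 points and √(0.05·0.95/1500) = 0.6 points. Model choice therefore adds about 2 points over a single test (8.0 − 5.7 = 2.3; 7.0 − 5.2 = 1.8). The interaction rows depend on the assumed count: independent tests would give 1 − 0.95⁶ = 26% and 1 − 0.95⁸ = 34%.

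**3. Dropout.** Expected loss is 40/240 = 16.7%. Simulating 240 patients with exponential dropout of one sixth, at 0.40 vs 0.215, power is about 81% for strict completers, about 84% if infections seen before dropout are kept, and about 85% for a log-rank test on all 240 (86% in a separate run). The gain in power is small. The bias from unequal loss was not quantified, because the documents give no dropout rates by arm.

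**4. Interim looks, only if infection were tested at 0.05 each time.** Information fractions are assumed.

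| Looks | Error |
|---|---|
| Three, month 6 final (1/3, 2/3, 1) | 10.7% |
| Three, month 6 final (1/6, 1/2, 1) | 11.9% |
| Three interims plus final, equal spacing | 12.6% |
| Three interims plus final, early looks | 13.9-14.9%; 15.6% with a first look at 2% of the information |
| Interims at 0.001, final at 0.05 | 5.0-5.2% |

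**The case against.** The trial is a pilot; Section 5.1 hopes to show feasibility and only possibly efficacy. Both 15.1 and 15.2 name logistic regression, and 15.1 contemplates an adjusted level of 0.005. On this view only detail is missing. Part of that stands: a model family is named and should be credited. But 6.1 aims to demonstrate an effect, 15.1 quotes 80% power, 16.4 treats the study as a covered trial, and the 0.005 scenario is not carried into 15.2.

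Four stronger readings are tempting, and the documents do not support them.

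- A reader might infer that the primary test is repeated at each interim look. Section 15.2 gives those looks a monitoring purpose, and 13.9 has a safety stopping rule only. Efficacy testing is not excluded, but neither is it planned. Month 6 is also the last visit in Table 1, so that look may itself be the final analysis.
- A reader might take 31-36% as the trial's error rate. It comes mostly from interaction tests, which do not test the primary hypothesis, and it scales with a count the plan does not give.
- A reader might infer a completers-only analysis. Section 15.1 says the whole sample will be used, and 9.4 seeks continued evaluation after discontinuation. Logistic regression can also use partly followed patients through imputation, weighting or discrete-time models. What is missing is a stated method.
- A reader might count the absent survival method as a source of false positives. It bears on bias and completeness and does not itself raise type I error.

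**Conclusion.** The point holds in a bounded form. Section 15.2 sets out a data-driven search and singles out no primary test, so control of the 5% level assumed in 15.1 is not specified. Under the assumed covariate sets, choosing among main-effect models gives about 7-8% false positives. Roughly 25-36% applies only if any hit among six to eight assumed interactions could be claimed.

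The mismatch between 15.1 and 15.2 on dropout is real. It is a bias risk of unknown size with a small effect on power. Interim inflation of about 11-12% (three looks) or 13-15% (three interims plus a final) is conditional on testing infection at 0.05 at every look, which the plan does not state.

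**What to change.** State one primary analysis in 15.2:

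- all randomised patients by assigned arm;
- stratified by or adjusted for dialysis site, which is the randomisation stratum;
- a fixed, named list of baseline covariates;
- two-sided 0.05;
- a method that uses partly followed patients as 15.1 intends, for example time to first documented infection through month 6, censored at last assessment, with death as a competing event.

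A logistic analysis with a declared rule for incomplete follow-up and death would also serve; the essential step is to fix one before infection data by arm are examined. Label all other models, trees, interactions and subgroup fits exploratory. State that interim looks make no efficacy comparison or, if they do, use two-sided 0.001 at each look and 0.05 at the end.

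The cost is mainly SAP wording. A single two-sided 0.05 test with 200 patients keeps 81.4% power. If the primary becomes a time-to-event analysis, 15.1 should restate its power on that basis. The real downside is less freedom to choose a model after seeing the data.

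A minor item: Section 13.9 says "The committee will meet at trial initiation and quarterly for the one-year duration of the study", which matches no 1-month look, so the two calendars should be reconciled.

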Subjects who report respiratory illness symptoms (see Appendix 1 for symptom questionnaire) at the designated inventory times (Table 1) or in the interval between those designated times will be tested for COVID-19 virus. If the COVID-19 assay is positive, this will complete the treatment phase of the research protocol for that individual. However, the subject will remain on study with continuation of the designated assessments to assess severity of disease (e.g., need for hospitalization, ICU management, mechanical ventilation, mortality).

In addition to infection with COVID-19, the following assessments will be collected and recorded at intervals in Table 1:

- Need for hospitalization
- Hospital length of stay
- ICU admission
- ICU length of stay
- Mechanical ventilation
- Mortality
- Incidence of secondary infections
- CD4, CD8, CD4/CD8.

Assessment for secondary infections will be documented in the CRF. Sites will be required to record all infections occurring from the time of enrollment until completion of the study 6 months after enrollment. Data will include the site of the infection, the evidence of infection, the organism cultured, and the antimicrobial susceptibility data.

The study will use the Inova Central Laboratory for conducting all laboratory investigations included in this study.

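### The count model for non-COVID-19 infections specifies no follow-up time, so incidence is understated and the arm ratio is biased if exits differ by arm

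*Combined protocol and SAP*

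**What the plan says.** Section 8.2 lists endpoint 9 as "Incidence of secondary non-COVID-19 infections (relapses, superinfections and new infections"), with no time unit or denominator. Section 15.1 names it as the example of a count outcome: "counts (e.g., occurrence of non-COVID-19 infections"). Section 11.1 sets the recording window: "Sites will be required to record all infections occurring from the time of enrollment until completion of the study 6 months after enrollment".

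Section 15.2 gives the model for such outcomes, "Poisson regression with an over-dispersion test or a general log-linear model, for count outcomes". No offset, person-time or rate is mentioned there or elsewhere. When sizing the trial, section 15.1 adds "The count variables can be modeled as continuous with appropriate transformation", again without an exposure term.

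Incomplete follow-up is foreseen. Section 15.1 enrols 240, "anticipating that 40 subjects will drop off study for any of a number of reasons", and continues "That will leave ~200 enrolled subjects with complete data availability". Section 9.4 says that patients who discontinue after randomisation are not replaced, and mortality is endpoint 11. No analysis set is defined. Section 15.1 does say that the whole sample will be used and that censored or missing data will be handled by a survival or fuller model. That remark is set against logistic regression and justified by power for the infection rates, so it gives no rule for counts.

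**The concern.** A log-link count model without an offset gives every patient the same exposure. A patient who leaves in week 3 with no infection then carries the same weight as one followed for six months with none. Two things follow if leavers are kept.

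- The reported incidence is too low in both arms.
- The ratio between arms is distorted whenever the number or timing of exits differs.

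A difference in exits is plausible here, but its direction is not known. Control patients receive no injections (section 10.1), so treatment burden could raise exits on Ta1. The survival benefit hypothesised for infected patients (section 6.2) would lower deaths on Ta1. At stake is a spurious finding, or a masked one, on a secondary endpoint.

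**Working it through.** **Plan's own figures.** The drop-out allowance reproduces: 200 / (1 − 40/240) = 240. There is no sample-size figure for the Poisson model; section 15.1 says that counts follow the continuous case (effect size 0.35, N = 201, 80% power). That figure reproduces with a one-sided 5% test (N = 202; power 79.8% at 201) but not two-sided (N = 258). This is a separate matter and does not affect what follows.

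**Inputs from the documents.** 240 patients randomised 1:1, so 120 per arm; 40 exits; infections counted over six months (26 weeks); treatment phase 8 weeks.

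**Assumptions, not in the documents.** The split of exits by arm; their timing; all leavers kept with their observed counts; a constant infection rate, equal in the two arms.

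Let m be the mean fraction of the 26 weeks that a leaver is observed.

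- Exits uniform over 26 weeks (mean three months): m = 0.5.
- Exits uniform over the first 8 weeks (mean 4 weeks): m = 4/26 = 0.154.

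**Step 1: understated incidence.** Observed share of the implied person-time = (200 + 40m)/240.

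- m = 0.5: 220/240 = 0.917, so 8% too low.
- m = 0.154: 206.15/240 = 0.859, so 14% too low.

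**Step 2: between-arm ratio with no effect.** With a exits on Ta1 and c on control, the expected ratio without an offset is (120 − a + am)/(120 − c + cm).

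| Exits Ta1/control | m = 0.5 | m = 0.154 |
|---|---|---|
| 20/20 | 110/110 = 1.00 | 103.08/103.08 = 1.00 |
| 25/15 | 107.5/112.5 = 0.956 | 98.85/107.31 = 0.921 |
| 30/10 | 105/115 = 0.913 | 94.62/111.54 = 0.848 |

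If control has more exits the ratios invert; for example 115/105 = 1.10. Timing alone also matters: with 20/20 exits, Ta1 exits in the first 8 weeks and control exits uniform, the ratio is 103.08/110 = 0.937.

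**Step 3: false-positive rate.** 20,000 simulated trials per scenario, Poisson counts, two-sided 5% Wald test, 0.5 to 1.0 infections per patient per six months (assumed).

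| Exits Ta1/control | Uniform, 26 weeks | First 8 weeks |
|---|---|---|
| 20/20 | about 5% | about 5% |
| 25/15 | 5.7% to 6.4% | 7.0% to 8.9% |
| 30/10 | 7.7% to 10.7% | 13.1% to 22.1% |

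With observed person-time as the denominator, the rate was 4.8% to 5.2% in every scenario. The simulation makes exit independent of infection, which favours the offset.

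**Step 4: completers only.** Follow-up is then about equal and the mechanism of steps 1 and 2 disappears. In its place, 40/240 = 17% of randomised patients and their infections are dropped, and the comparison is no longer between the randomised groups. The documents give nothing from which to size that bias.

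**The case against.** The strongest reply is that this is silence, not a wrong method. Poisson and log-linear models routinely carry an offset, the endpoint is called an incidence, and nothing in the plan excludes person-time. That is correct. A reader might infer that the plan counts every leaver as six full months; the documents do not say so. The sentence about roughly 200 patients with complete data could point to a completer analysis, while the statement that all the sample will be used points the other way. What stands is that neither route is sound without a stated rule.

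Second, the bias in the ratio needs imbalance, and the documents give neither split nor timing. A reader might take the 13% to 22% false-positive rate as the expected size. It is not: it needs a 3:1 split with every exit in the first 8 weeks and no infection data afterwards. A 25/15 split spread over six months leaves the error near 6%.

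Third, stopping injections is not leaving the study. Section 9.4 has the investigator ask such patients to continue evaluations, and section 10.1 keeps COVID-19-positive patients under assessment. This should reduce lost follow-up, but it cannot prevent deaths or refusals.

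Fourth, the sentence on transformed counts belongs to the sample-size justification and closes by comparing sample sizes. It should not be read as a competing analysis plan.

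**Conclusion.** The point holds as a minor improvement to secondary endpoint 9 of 11 in a self-described pilot. The plan names a count model and foresees incomplete follow-up, but does not connect the two. If leavers are kept without an offset, incidence is understated by about 8% to 14%, depending on when they leave. The ratio with no effect is about 0.96 (25/15) or 0.91 (30/10) with exits at three months on average, 0.85 for 30/10 with exits in the first 8 weeks, and 1.00 when exits match in number and timing. These ratios rest on assumed splits and timing, 120 per arm and a constant rate.

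A reader might go further and infer that the trial will make Ta1 look protective. The documents do not support that: they do not say which arm will lose more patients, and the reasons for expecting a difference point in opposite directions.

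**What to change.** In section 15.2, specify for count outcomes:

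- an over-dispersed Poisson or negative binomial model with treatment and dialysis site, in all randomised patients;
- infections counted from randomisation, with offset log(time from randomisation to the earliest of death, last contact or month 6);
- results reported as infections per patient-year observed.

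Section 11.1 records infections "from the time of enrollment until completion of the study 6 months after enrollment". Counting for this analysis from randomisation gives numerator and offset the same start. In section 15.1, note that treating counts as transformed continuous variables is a sample-size approximation only.

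The cost is a little extra analysis work and a check of the CRF. Section 9.4 lists the discontinuation date, the last-dose date and the reason for death, but not the date of death or of last contact, so those two should be confirmed as fields. The offset also has a limit: it assumes that exit is unrelated to infection risk given the covariates, which may fail where an infection leads to death. That limitation should be stated with the result.
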